#### **4. STUDY POPULATION**

[figure not shown]
##### **4.1 Definition of study groups**

An algorithm will be developed to reliably identify eligible subjects from administrative database SDO. The algorithm will apply specific criteria to patients collected in administrative databases from January 2017 to December 2017. It will be developed as the combination of ICD-9-CM codes with other criteria. Selection of codes and criteria was based on a discussion between senior Oncologists with expertise in lung cancer and the outcome research working group at IRST.

A first data extraction from the administrative database will be performed to identified potential study subjects. These data are related to patients with at least one hospitalization due to diagnosis of malignant tumors of trachea, bronchi and lungs between January and December 2017 using the International Classification of Diseases, 9th EDITION, (ICD-9-CM codes: 162\* in all position of diagnosis codes).

The following criteria will be applied to obtained patients, to exclude prevalence NSCLC cases (incident cases in 2014-2016 period), patients with mesothelioma (cod 163\*) and SCLC patients in order to obtain the correct population.

- Only NSCLC incident cases in 2017 will be considered, excluding prevalence cases that had the same diagnosis in the 3 years before the period of interest (2014-2016). Patients with at least one hospitalization due to diagnosis of malignant tumors of trachea, bronchi and lung according to ICD-9CM 162\* in the 3 years prior to the first index hospitalization on the year of evaluation (2017) will be excluded

- Patients with at least one hospitalization due to malignant tumor different than tumors of trachea, bronchi and lungs (ICD-9CM 140\*-161\* or 163\*- 195\* or 200\* - 208\* or V.10\* excluding V10.11 and V10.12), in the 3 years previous 2017 should be excluded.
- All patients with at least one ATC Code L01CB01
- Etoposide (VP-16) therapy administration in the 180 days following the first hospitalization index will be excluded.

After criteria application, the final population shall include only NSCLC patients.

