## **3. STUDY DESIGN**

This is a multi-center, observational study involving retrospective collection of NSCLC patients information. All consecutive patients who had a newly diagnosis of NSCLC in 2017 from healthcare administrative database and received at least one anti-cancer drug treatment between January 2017 and December 2017, identified through the proposed algorithm, will be considered. All data needed for KPI calculation, even if they fall outside January-December 2017 period, will be collected. The end of data collection will be defined as patient death or 30 June 2018, whichever came first.

A set of potential KPIs had been developed from a panel of experts (clinicians, IT experts etc..) to investigate the appropriateness of activities within NSCLC care pathway, with a special focus on the use of immunotherapy.

The eligible population and data will be gathered retrospectively through an algorithm from administrative databases (SDO, REM, ASA, FED, AFT, ADI, SDHS-hospice).

Administrative data will be used as unique resource:

- to identify patients cohort;
- to measure KPIs along care pathway ;

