### 5.2 Key performance indicators for monitoring care pathway in NSCLC patients

The following key performance indicators (KPIs) will be measured to investigate the appropriateness of NSCLC patient care pathways, with a special focus on the use of immunotherapy.

[figure not shown]
BOZZA - KPI -	
1	
Percentage of patients who performed biopsy within 7 days from the date of examination prescription
 
NUM: Number of patients who performed biopsy within 7 days from prescription; DEN: Total number of patients identified by the algorithm who performed biopsy;

2	
Percentage of mNSCLC patients at diagnosis
 
NUM: Number of patients with metastases (presence of one of the following codes (197*,198*,199*) in all position of diagnosis codes for index hospitalization); DEN: Total number of patients identified by the algorithm;

3	
Percentage of major surgical resections within the year of analysis.
 
NUM: Number of patients who underwent to lung cancer major surgical resection; DEN: Total number of patients identified by the algorithm;

	
To identify major surgical procedures for lung, the following codes of ICD-9-CM classification will be identified:
 
  
 ICD-9-CM coding related to major surgery on lung	
   
 32.01	ENDOSCOPIC EXCISION OR DESTRUCTION OF LESION OR TISSUE OF BRONCHUS	
 
 32.29	OTHER LOCAL EXCISION OR DESTRUCTION OF LESION OR TISSUE OF LUNG	
 
 32.3	SEGMENTAL RESECTION OF LUNG	
 
 32.4	LOBECTOMY OF LUNG	
 
 32.5	COMPLETE PNEUMONECTOMY	
 
 34.6	SCARIFICATION OF PLEURA	
  
	ICD-9-CM coding related to major surgery on lung		32.01	ENDOSCOPIC EXCISION OR DESTRUCTION OF LESION OR TISSUE OF BRONCHUS	32.29	OTHER LOCAL EXCISION OR DESTRUCTION OF LESION OR TISSUE OF LUNG	32.3	SEGMENTAL RESECTION OF LUNG	32.4	LOBECTOMY OF LUNG	32.5	COMPLETE PNEUMONECTOMY	34.6	SCARIFICATION OF PLEURA
ICD-9-CM coding related to major surgery on lung															
32.01	ENDOSCOPIC EXCISION OR DESTRUCTION OF LESION OR TISSUE OF BRONCHUS														
32.29	OTHER LOCAL EXCISION OR DESTRUCTION OF LESION OR TISSUE OF LUNG														
32.3	SEGMENTAL RESECTION OF LUNG														
32.4	LOBECTOMY OF LUNG														
32.5	COMPLETE PNEUMONECTOMY														

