### **7.3 Data analysis**

For primary objective, for each indicator, the proportion of patients who receive the procedure, in the defined time window, among those eligible will be calculated. Descriptive statistics as arithmetic mean and standard deviation (SD) as well as median value and minimum–maximum statistics will be presented for KPI related to average time. Two-sided 95% confidence interval (95% CI) will be reported as appropriate and specified for KPI expressed as proportion. For secondary objective, the validity of algorithm will be evaluated by individual matching among cases retrieved from administrative database and medical chart obtained from IRST. Following definition will be used to explain this objective: NSCLC cases appearing as incident cases in administrative database, but not in IRST clinical chart will be considered as false positive and those appearing in IRST clinical chart but not in administrative database will be considered as false negatives.

Sensitivity will be defined as the percentage of NSCLC cases correctly identified by the algorithm and calculated as the proportion among NSCLC cases identified both in administrative database and IRST clinical chart ('true positive' cases) and all cases identified as NSCLC cases from IRST clinical chart ('true positive' + 'false negative' cases). Positive predictive value will be defined as the percentage of NSCLC patients identified from IRST clinical chart were really NSCLC. This proportion will be calculated as the proportion among NSCLC cases identified both in administrative database and IRST clinical chart ('true positive' cases) and all cases identified as NSCLC cases from administrative database ('true positive' + 'false positive' cases).

Likewise, specificity and negative predictive value will be calculated, and exact (Clopper-Pearson) 95% confidence limits for binomial distribution will be applied.

Statistical analysis will be performed using Stata software 15.1/SE for Windows (Stata Corp LP, USA).

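### Cohort entry needs a 2017 hospital record that a lung resection normally supplies, so KPI 3 read as a rate for all new NSCLC is probably too high, by an unknown amount

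*Protocol*

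**What the plan says.** **Entry.** Section 4.1 opens with "An algorithm will be developed to reliably identify eligible subjects from administrative database SDO" (SDO is the hospital discharge card). The first extraction takes "patients with at least one hospitalization due to diagnosis of malignant tumors of trachea, bronchi and lungs between January and December 2017", with ICD-9-CM code 162* accepted "in all position of diagnosis codes". Section 3 lists outpatient, drug, home-care and hospice databases as well, but 4.1 gives no route into the cohort through them. Section 4.3 admits only patients found by the algorithm and fixes age at the first index hospitalization. Section 7.1 analyses the patients identified under 4.1.

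**Described population.** Section 3 speaks of "All consecutive patients who had a newly diagnosis of NSCLC in 2017 from healthcare administrative database" and adds a second condition, that they "received at least one anti-cancer drug treatment between January 2017 and December 2017". It also says that the patients are identified through the algorithm. The drug condition does not appear in 4.1, 4.3 or 7.1. The KPI 11a denominator is the drug-treated part of the algorithm cohort, which implies that the cohort also holds untreated patients.

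**KPI 3 (section 5.2).** The title is "Percentage of major surgical resections within the year of analysis" and the ratio is "NUM: Number of patients who underwent to lung cancer major surgical resection; DEN: Total number of patients identified by the algorithm".

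**Validation.** Section 7.3 states "Sensitivity will be defined as the percentage of NSCLC cases correctly identified by the algorithm". It gives one overall value, at IRST only, with positive predictive value, specificity and negative predictive value alongside. Section 4.2 says that the 4.1 criteria are applied to the IRST electronic records.

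**The concern.** A patient diagnosed and treated wholly as an outpatient in 2017 cannot enter the cohort. A patient who has a lobectomy in 2017 will normally have a discharge record coded 162*, and that record is enough for entry. The numerator event of KPI 3 thus helps a patient into its denominator, while other patients depend on being admitted for another reason.

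The primary objective is to assess quality of care among the three sites. If the share of non-resected patients who are admitted differs between sites, KPI 3 could differ with identical surgical practice. KPIs 7, 11, 15 and 16 would likewise describe admitted patients, while section 3 reads as a description of all new cases. One overall sensitivity cannot show whether capture differs by resection status. If the hospitalization criterion is carried into the chart list, never-admitted patients are not counted as missed at all.

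**Working it through.** The protocol states no expected KPI 3 value and no formal sample size, so there is no figure to reproduce. The figure of about 400 patients in section 7.2 is a feasibility count.

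**Inputs.** From the protocol: the entry rule (4.1), the KPI 3 ratio (5.2), the drug condition (3) and n of about 400 (7.2). Assumed, because the protocol gives none of them:
- p, the true resection share among all incident NSCLC;
- h, the share of non-resected patients with a qualifying 2017 admission;
- r, the share of resected patients captured;
- d_r and d_n, the shares given an anti-cancer drug in 2017 among resected and non-resected patients.

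**Step 1: 4.1 alone, all resected patients captured (r = 1).** KPI 3 reads p / [p + (1 − p)h], which exceeds p whenever h < 1.

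| p | h = 0.95 | h = 0.90 | h = 0.80 | h = 0.70 | h = 0.50 |
|---|---|---|---|---|---|
| 10% | 10.5% | 11.0% | 12.2% | 13.7% | 18.2% |
| 20% | 20.8% | 21.7% | 23.8% | 26.3% | 33.3% |
| 30% | 31.1% | 32.3% | 34.9% | 38.0% | 46.2% |

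For example, p = 20% and h = 0.80 give 0.20 / (0.20 + 0.64) = 23.8%. For scale, the 95% confidence half-width at 20% with n = 400 is 1.96 × √(0.2 × 0.8 / 400) = 3.9 percentage points. The bias is 0.8 points at h = 0.95 and 3.8 points at h = 0.80. The confidence interval does not reflect it.

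**Step 2: resected patients not all captured.** KPI 3 reads pr / [pr + (1 − p)h], which is upward only if r > h. With p = 20%:
- r = 0.95, h = 0.80 gives 22.9%;
- r = 0.90, h = 0.90 gives 20.0%;
- r = 0.90, h = 0.95 gives 19.1%.

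**Step 3: the section 3 drug condition applied (r = 1).** KPI 3 reads p·d_r / [p·d_r + (1 − p)·h·d_n], which is upward only if d_r > h·d_n. With p = 20%, h = 0.80 and d_n = 0.70, the threshold is d_r = 0.80 × 0.70 = 0.56.
- d_r = 0.40: 0.080 / (0.080 + 0.448) = 15.2%, too low.
- d_r = 0.60: 0.120 / (0.120 + 0.448) = 21.1%, too high.

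**Step 4: what a correction must contain.** Write K for the observed KPI 3, and Se and PPV for sensitivity and positive predictive value, with suffix r for resected and n for non-resected. Assume p = 20%, Se_r = 1, Se_n = 0.80, PPV_r = 1 and PPV_n = 0.85. Flagged non-resected patients are 0.80 × 0.80 / 0.85 = 0.753 per incident case, so K = 0.20 / 0.953 = 21.0%.
- Sensitivities only: (K/Se_r) / [K/Se_r + (1 − K)/Se_n] = 0.210 / (0.210 + 0.988) = 17.5%, further from the truth than K.
- Both measures: (K·PPV_r/Se_r) / [K·PPV_r/Se_r + (1 − K)·PPV_n/Se_n] = 0.210 / (0.210 + 0.840) = 20.0%, the true value.

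**The case against.** A reader might infer that resected patients are always captured, that only non-resected patients can be missing, and that KPI 3 is therefore overstated without qualification. The text does not support that.
- The section 3 drug condition, if applied, removes patients treated by surgery alone and can reverse the direction (step 3).
- Resected patients can also be lost through the prior-cancer and etoposide exclusions in 4.1, the residence exclusion in 4.4, or an admission without a 162* code.
- That every KPI 3 event is an admission is itself an inference. KPI 3 names no setting (KPI 4 does), and its code list includes an endoscopic procedure, 32.01.
- The only filter in 4.1 for small-cell cases is etoposide within 180 days. Small-cell patients who escape it stay in the denominator and, if mostly unresected, pull KPI 3 down.

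These points stand, and they limit the claim to a likely direction under 4.1.

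It can also be said that KPI 3 is correct for its literal denominator, and that section 3 itself ties the population to the algorithm. That is right, so the error arises only when the figure is read as a rate for all new NSCLC. The section 3 wording invites that reading.

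On size, one admission with 162* in any diagnosis position suffices, so h may be close to 1 and the bias small. Nothing in the protocol shows that h differs between sites, so a between-site distortion is possible but not demonstrated.

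Lastly, section 7.3 already counts chart cases absent from the administrative data as false negatives, and splitting accuracy by subgroup is often left to an analysis plan. The split alone would not be a finding. The entry rule, the section 3 description and the possible use of the 4.1 criteria on the charts are fixed in the protocol itself.

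**Conclusion.** The concern holds in a limited form. Under 4.1 as written, capture can depend on the KPI 3 event, and KPI 3 read as a rate for all incident NSCLC is likely biased upward. This requires that resected patients are captured more completely than others (r > h) and that residual small-cell cases do not offset the effect. The size cannot be computed from the protocol. With all resected patients captured and a true share of 10% to 30%, the excess would be about 0.5 to 1.1 points at h = 0.95 and 2.2 to 4.9 points at h = 0.80; all these shares are assumptions. If the section 3 drug condition applies, the direction is open, so sections 3 and 4.1 must be reconciled before any direction is claimed. The planned single sensitivity cannot settle the matter.

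**What to change.** 1. Reconcile section 3 with 4.1, 4.3 and 7.1 on the drug condition. In section 3, section 7.1 and the conclusions, state the population as incident NSCLC with at least one 2017 hospital discharge record coded 162*, so that no KPI is read as a rate for all new NSCLC.
2. In 4.2 and 7.3, build the IRST chart reference list without the hospitalization criterion. Report sensitivity and positive predictive value separately for cases with and without lung resection.
3. If a corrected KPI 3 is given for IRST, use both accuracy measures as in step 4: (K·PPV_r/Se_r) / [K·PPV_r/Se_r + (1 − K)·PPV_n/Se_n]. Label it a sensitivity analysis for IRST only; the other two sites have no chart data to support it.

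Cost: a narrower population claim, some rewording, a yes/no resection item for the IRST chart cases, and extra chart listing if never-admitted IRST cases are not already included.

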#### **4.4 Exclusion criteria**

The subjects who lives outside the regional territory of competence will be excluded from analysis due to the difficulty in obtaining the medical data.

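### A look-back holding only V10.11 or V10.12, with no 162 code, escapes both cancer-history exclusions in section 4.1, so that patient is kept as a 2017 incident case

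*Protocol*

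**What the plan says.** Protocol section 3 defines the cohort as "All consecutive patients who had a newly diagnosis of NSCLC in 2017 from healthcare administrative database", with at least one anti-cancer drug treatment in that year. Section 4.1 repeats the aim: "Only NSCLC incident cases in 2017 will be considered, excluding prevalence cases that had the same diagnosis in the 3 years", a window that it names as 2014-2016.

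Two rules in section 4.1 deal with cancer history.

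- **First rule (earlier lung cancer).** It applies to patients hospitalised for "malignant tumors of trachea, bronchi and lung according to ICD-9CM 162", and those with such an admission "in the 3 years prior to the first index hospitalization on the year of evaluation (2017) will be excluded". No V10 code is named.
- **Second rule (other cancers).** It excludes patients with "at least one hospitalization due to malignant tumor different than tumors of trachea, bronchi and lungs" in the three years before 2017. Its code list is 140-161, 163-195, 200-208 and V10, "excluding V10.11 and V10.12".

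The remaining criteria are the etoposide rule (4.1), the age limit (4.3) and residence (4.4: "The subjects who lives outside the regional territory of competence will be excluded from analysis"). None of them concerns earlier lung cancer.

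**The concern.** The carve-out sits in a rule about tumours other than trachea, bronchi and lung. The protocol thus itself treats V10.11 and V10.12 as the history codes for those sites, and no outside code list is needed to see this. Removing them from the second rule suits that rule's scope. The difficulty is that the first rule, where they would belong, does not take them up.

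The result is uneven. A history code for any other cancer in the look-back is enough to exclude. A history code for lung cancer, the disease whose prevalent cases the algorithm is meant to remove, is not.

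KPIs 2 and 3 (section 5.2) both use all patients identified by the algorithm as denominator. KPI 2 reads metastasis codes at the index hospitalisation as metastatic disease at diagnosis, so a relapse admitted in 2017 could be counted as metastatic at first diagnosis. KPI 3 counts major resections within the year of analysis, so a patient operated on earlier could add to the denominator without adding to the numerator. An error of this kind is systematic, and a confidence interval does not show it.

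**Working it through.** There is no sample-size or power figure to reproduce. Section 7.2 says none was calculated and gives about 400 patients as a feasibility count. The check is therefore of the code logic, followed by an illustration of size.

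**Step 1: apply the two rules literally to look-back codes.** Every patient is assumed to have a 162 admission in 2017 and to meet the other criteria.

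| Codes in the look-back | First rule | Second rule | Result |
|---|---|---|---|
| none | no | no | kept |
| 162.9 | yes | no | excluded |
| V10.11 only | no | no | **kept** |
| V10.12 only | no | no | **kept** |
| V10.11 and 162.9 | yes | no | excluded |
| V10.11 and V10.3 | no | yes | excluded |
| V10.3 only | no | yes | excluded |
| 163.9 | no | yes | excluded |
| V10.11 and 197.0 | no | no | **kept** |

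The last row arises because 196-199 lies outside the second rule's ranges. The gap is therefore V10.11 or V10.12 with no 162 code and no code that triggers the second rule.

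**Step 2: how many patients.** The protocol gives no frequency. Let p be the share of the 400 who are kept through this gap, assumed to be 1% to 5%.

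- p = 1%: 400 × 0.01 = 4 patients, leaving 396 if removed.
- p = 5%: 400 × 0.05 = 20 patients, leaving 380 if removed.

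**Step 3: effect on KPIs 2 and 3.** The base rates are assumptions: 60% metastatic and 25% resected among true incident cases. The extreme case is that every carried-over patient is coded metastatic and none is resected in 2017.

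- KPI 2 = (1 − p) × 60% + p × 100%. At 1% this is 59.4 + 1.0 = 60.4%. At 5% it is 57.0 + 5.0 = 62.0%. The shift is +0.4 to +2.0 points.
- KPI 3 = (1 − p) × 25%. At 1% this is 24.75%. At 5% it is 23.75%. The shift is −0.25 to −1.25 points.

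The KPI 2 shift equals p × (100% − base rate), so it depends on the assumed 60%. At 5% carry-over and a base of 50%, for example, it would be 2.5 points.

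**Step 4: compare with sampling error at n = 400.**

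- KPI 2: 1.96 × √(0.60 × 0.40 / 400) = 1.96 × 0.0245 = 4.8 points.
- KPI 3: 1.96 × √(0.25 × 0.75 / 400) = 1.96 × 0.0217 = 4.2 points.

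Even the extreme shifts are smaller than the half-widths.

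**The case against.** **The gap is narrow.** Most patients with earlier lung cancer treated in hospital in 2014-2016 would be expected to have a 162 discharge, and the first rule removes them. Those who slip through also need a 162 admission in 2017 and must meet the etoposide, residence and drug-treatment conditions. This stands. A reader might infer that patients with a coded lung-cancer history enter the cohort in general, but the first rule shows otherwise.

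**Many of those affected were probably diagnosed before 2014.** Section 4.1 describes prevalent cases as those incident in 2014-2016, and any fixed washout misses older ones. This weakens the charge that the rule defeats its own definition of prevalence. It does not remove the conflict with section 3, because an older case is not a new diagnosis in 2017 either. The second rule, moreover, already uses history codes to reach older cancers at other sites.

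**A history code followed by 162 may be a second primary.** This is possible, and the codes cannot separate it from relapse. The protocol states no such reason for keeping these patients, and the first rule already drops second primaries that follow an earlier 162 admission.

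**Validation could find them.** Section 7.3 counts as false positives those who appear as incident in the administrative data but not in the chart. Section 4.2 then allows the algorithm to be revised, and section 2.2 carries it to the other sites. This is a partial safeguard. Chart review is at IRST only, section 4.2 frames the comparison as NSCLC versus non-NSCLC (on which a relapse could count as agreement), and no rule for the two codes is written.

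**The background recurrence figure.** Section 1 cites 30% to 75% recurrence after complete resection, mostly metastatic. A reader might infer that relapsed carry-overs are common. The figure says nothing about how often a look-back holds V10.11 or V10.12 without 162, and a patient resected in 2014-2016 would ordinarily have a 162 discharge and be excluded already.

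**Other KPIs.** A reader might also expect KPIs 1, 7, 10 and 13 to be distorted. The protocol supports neither a direction nor a size for that. KPI 1, for instance, runs from prescription to biopsy and does not depend on when the disease began.

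**Conclusion.** The point holds as a specification gap. Read literally, section 4.1 keeps a patient whose only look-back evidence of earlier lung cancer is V10.11 or V10.12, contrary to the requirement of a new diagnosis in 2017 and out of line with how every other coded cancer history is handled.

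Its size cannot be derived from the protocol. On an assumed 1% to 5% of 400 patients, 4 to 20 would be kept. With assumed base rates of 60% and 25%, all carry-overs metastatic and none resected, the shift is at most about 2 points in KPI 2 and about 1 point in KPI 3. That is within sampling error and does not show that the KPI results would be materially misleading. The case for acting is that the rule is inconsistent and the repair is cheap.

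**What to change.** In the first exclusion rule of section 4.1, exclude patients with V10.11 or V10.12, in any diagnosis position, in the three-year look-back, alongside those with a 162 code. Report the number removed by this addition, and give KPIs 2 and 3 with and without them.

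The cost is one line in the algorithm and a short amendment. No new data are needed, since the second rule already searches V10 codes in the look-back. On the assumed range the cohort would fall from 400 to between 396 and 380. A few true second primaries would be lost, as the first rule already does for patients with an earlier 162 admission, and the with-and-without report lets a reader see what that exclusion changes.

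### The mesothelioma exclusion in Section 4.1 stops at the end of 2016, so a patient coded with both 162 and 163 in 2017 stays in a cohort meant to be NSCLC only

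*Protocol*

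**What the plan says.** All the relevant text is in Protocol Section 4.1.

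- **Purpose.** The criteria are applied "to exclude prevalence NSCLC cases (incident cases in 2014-2016 period), patients with mesothelioma (cod 163\*) and SCLC patients in order to obtain the correct population".
- **Entry.** Candidates have at least one admission between January and December 2017 with a 162 code "in all position of diagnosis codes". A second tumour code on the same discharge record is therefore possible.
- **Other-tumour criterion.** The codes are "140\*-161\* or 163\*- 195\* or 200\* - 208\* or V.10\* excluding V10.11 and V10.12". The range 163 to 195 makes this the only criterion that reaches mesothelioma. Its window is hospitalizations "in the 3 years previous 2017 should be excluded".
- **Prior lung cancer criterion.** One sentence gives a fixed window, "excluding prevalence cases that had the same diagnosis in the 3 years before the period of interest (2014-2016"). The next gives a rolling one, "in the 3 years prior to the first index hospitalization on the year of evaluation (2017) will be excluded".
- **Claimed result.** "After criteria application, the final population shall include only NSCLC patients".

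Section 4.3 makes identification by this algorithm an inclusion criterion. Section 4.2 provides for chart validation at IRST and for later revision of the algorithm's definitions.

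**The concern.** The study counts cases incident in 2017, so a new mesothelioma in a candidate patient would also tend to be coded in 2017. The rule meant to remove mesothelioma does not look at that year. It removes only patients whose 163 code dates from 2014 to 2016.

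Two things are at stake. First, a retained mesothelioma patient is a false positive, which lowers the positive predictive value and the specificity defined in Section 7.3. Second, KPIs 2, 3, 7, 15 and 16 have all patients identified by the algorithm as their denominator, so the same patient enters those proportions. Modena and Reggio Emilia have no chart check (Section 6.3), so the written rule is the only filter there.

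**Working it through.** The plan gives no figure to reproduce. Section 7.2 states that no formal sample size was calculated and gives about 400 patients as a feasibility count. The check is therefore to write the rules out in dates and run test patients through them.

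**Inputs (Section 4.1).** Entry: 162 on any 2017 admission. Exclusion on 163: admission dated 1 January 2014 to 31 December 2016. The test patients are assumed to trigger no other exclusion (no earlier tumour admission, no etoposide within 180 days after index).

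**Test patients**

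| 163 coded | Index 162 admission | Result under the text |
|---|---|---|
| 15 March 2016 | 10 October 2017 | excluded |
| 15 March 2017 | 10 October 2017 | kept |
| on the index record | 10 October 2017 | kept |
| after index, in 2017 | 10 October 2017 | kept |
| in 2017, no 162 code | none | never enters |

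The second to fourth rows contradict the stated purpose. The last row shows why the group is limited to double-coded patients.

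**Unscreened time before index.** Days unscreened = index date minus 1 January 2017. This is 0 for an index on 1 January and 364 for one on 31 December. The mean is (0 + 364)/2 = 182 days if index dates are uniform over 2017, which is an assumption. The index admission and all time after it are unscreened for everyone.

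**Number of patients.** The documents give no rate of joint 162 and 163 coding. As an assumed range: 400 × 0.005 = 2 and 400 × 0.05 = 20.

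**Effect on a KPI.** Take an all-patient denominator of 400 containing k mesothelioma patients. Let p0 be the true proportion among the NSCLC patients and p1 the proportion among the k. The reported proportion is [(400 − k)p0 + k·p1]/400, so the shift is (k/400)(p1 − p0). Its absolute value cannot exceed k/400: 2/400 = 0.5 percentage points to 20/400 = 5 percentage points over the assumed range. It is smaller unless the two groups differ completely.

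**The two look-backs for prior 162.** For an index on 10 October 2017 the rolling window opens on 10 October 2014. A 162 admission on 15 March 2014 is inside the fixed window and outside the rolling one. Over all index dates the fixed window reaches 0 to 364 days further back. The rolling window adds only the 2017 days before index, and these cannot hold a 162 admission because the index is the first one in 2017. If both sentences are applied as exclusions, the fixed window decides and there is one cohort.

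**The case against.** The best defence is that the algorithm is not final. Section 4.1 says it will be developed, and Section 4.2 says its definitions will be revised to remove disagreement with the charts. A mesothelioma patient brought in by a 162 code is the kind of false positive that this comparison should show. That stands in part, but the check exists only at IRST and the protocol states no corrected rule. Section 4.2 also describes applying the Section 4.1 criteria to the electronic records, so the same window could carry over into the chart classification.

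It is also fair to say that few patients can be affected and that their number is unknown. That stands in full and limits the weight of the point.

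A reader might infer three stronger claims, and the documents do not support them:

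- **That the two look-backs for 162 produce different cohorts.** They do so only if an analyst drops one of the two stated exclusions. This is loose drafting.
- **That any other primary tumour first coded in 2017 should also be removed.** Section 4.1 names prevalent NSCLC, mesothelioma and SCLC as the groups to remove. A patient with another primary first coded in 2017 can be a genuine incident NSCLC case, and nothing in the section says otherwise.
- **That KPI 3 is distorted because its surgery list includes 34.6 (scarification of pleura).** This would need the few double-coded patients also to carry that procedure. Whether 34.6 belongs in the list is a separate question that does not depend on this window.

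**Conclusion.** The point holds in a narrow form. Section 4.1 promises a cohort free of mesothelioma, and its only criterion on 163 does not cover the year in which the cohort is formed. Patients with both 162 and 163 coded in 2017 are kept. This follows from the text alone.

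The size does not. The 2 to 20 patients, and the ceiling of 0.5 to 5 percentage points on an all-patient KPI, rest on an assumed share of double-coded patients and on about 400 identified patients. The true effect is probably near the lower end or below it, and a reader should not conclude that the KPIs are materially biased. The correction is worth making because the rule fails its own stated purpose and is cheap to repair. The look-back wording for prior 162 is a minor alignment.

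**What to change.** 1. Give 163 its own criterion: exclude a patient with 163 in any admission from 1 January 2014 up to the index admission, on the index admission, or within a stated number of days after it. A fixed number of days is better than the remainder of 2017, which would give a January index about 12 months of screening and a December index almost none. For example, 180 days after an index on 31 December 2017 ends on 29 June 2018, inside the 30 June 2018 limit in Section 3. Section 5 confines the data to 2017, so it would have to be reconciled with Section 3.
2. Leave the etoposide criterion as it is. It runs for 180 days after index, and a single window for all exclusions that closed before index would cancel it.
3. State one look-back for prior 162, for example 1 January 2014 to the day before index, in place of the two wordings.

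**Cost.** An amendment with ethics committee approval and a date condition in the extraction code. The existing rules already require 2014–2016 discharge records and the 2017 extraction; only a post-index period running into 2018 would need later ones. Metastatic NSCLC is not affected, since the codes used in KPI 2 (197, 198, 199) are outside the exclusion. The downside is that a few double-coded patients who truly have NSCLC may be excluded, which slightly lowers sensitivity. The IRST validation can count them.
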